**Randomized Trial of Femoral Vein Hemostasis After Ablation for Atrial Fibrillation with
manual pressure versus a Figure of 8 suture.**

Principal Investigator
S. [name]

Sub-Investigator(s)
[name], MD
[name], MD
[name], MD
[name], MD
[name], MD
[name], MD
[name], MD
[name], MD
[name], MD

Sponsor
NA

Site of Investigation
IFH

Date of Protocol
02 November 2016

ABSTRACT

Title: Randomized Trial of Femoral Vein Hemostasis After Ablation for Atrial Fibrillation with manual pressure versus a Figure of 8 suture.

Short Title: Femoral Vein Hemostasis.

Rationale: Patients who undergo ablation for atrial fibrillation typically have 2 sheaths placed in each groin, including a large sheath when the Cryo Balloon is used for pulmonary vein isolation. During the procedure, heparin is administered to maintain a target ACT > 300 seconds. At the conclusion of the procedure, the venous sheaths are removed and hemostasis is obtained. There are at least 2 ways of obtaining hemostasis after venous access. In the manual hemostasis approach, an ACT is checked and protamine is administered. The ACT is rechecked 20" later, and if < 220 msec, the sheaths are pulled and hemostasis is achieved with manual pressure (Manual Hemostasis Group). Another conventional approach is to place a Figure of 8 suture around the sheaths in each groin to achieve hemostasis as the sheaths are removed, and therefore obviate the need for assessment of the ACT, protamine administration, and manual pressure (Figure of 8 Group).

Objectives: The goal of this study is to compare the safety and efficacy of obtaining hemostasis after an ablation for atrial fibrillation with the Manual Hemostasis Technique versus with the Figure of 8 Technique.

Study Type: This is a non-blinded, prospective, randomized trial.

Study Design: Number and types of subjects to be enrolled, study location, study duration, inclusion/exclusion criteria.

100 (50 in each group) patients undergoing Cryo balloon ablation for ablation of atrial fibrillation will be randomized to the Manual Hemostasis Group or to the Figure of 8 Group for venous hemostasis. Clinical characteristics, medications, procedure duration, heparin dosage, and post procedure anticoagulation will be collected. Follow up will end when the patient is seen in the office one month after the ablation procedure.

The study location will be the EP Laboratories at IFH, and the EP MDs outpatient offices.

All patients undergoing ablation for atrial fibrillation with the Cryo Balloon will be eligible to participate. Any patient who is under age 18 years of age, pregnant, or with an untreated DVT(s) will be excluded from participation.

Study Methodology: Summarize study treatment/interventions as well as if there is a control group/randomization. Identify primary and secondary outcomes.

The primary short term study endpoints will be the time required to obtain hemostasis, and for the time required from the completion of the ablation portion of the procedure until the patient leaves

the EP Lab. Secondary end points include groin complications including bleeds, additional pressure required for hemostasis, hematoma, pseudoaneurysm, and transfusion.

Statistical Methodology: Continuous variables will be expressed as the mean +/- SD. Univariate comparisons will be performed on continuous variables with either paired T test, unpaired T test or analysis of variance, as appropriate. Categorical variables will be compared with Chi-square analysis. Statistical significance will be considered present with a p value ≤ 0.05 .

1. INTRODUCTION

1.1. Specific Aims

The goal of this study is to compare the safety and efficacy of obtaining hemostasis after an ablation for atrial fibrillation (AF) with the Manual Hemostasis Technique versus with the Figure of 8 Technique.

Patients who undergo ablation for AF typically have 2 sheaths placed in each groin, including a large sheath when the Cryo Balloon is used for pulmonary vein isolation. During the procedure, heparin is administered to maintain a target ACT > 300 seconds. At the conclusion of the procedure, the venous sheaths are removed and hemostasis is obtained. There are at least 2 ways of obtaining hemostasis after venous access. In the manual hemostasis approach, an ACT is checked and protamine is administered. The ACT is rechecked 20" later, and if < 220 msec, the sheaths are pulled and hemostasis is achieved with manual pressure (Manual Hemostasis Group). Another approach is to place a Figure of 8 suture around the sheaths in each groin to achieve hemostasis as the sheaths are removed, and therefore obviate the need for assessment of the ACT, protamine administration, and manual pressure (Figure of 8 Group).

1.2. Hypothesis

The hypothesis of this study is that the Figure of 8 Technique to obtain hemostasis after Cryoballoon ablation for AF will take less time, and be associated with a lower frequency of groin complications.

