3.4.2. Secondary outcomes

Secondary end points include groin complications including bleeding, hematoma, pseudoaneurysm, and transfusion.

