4. STATISTICAL CONSIDERATIONS/DATA ANALYSIS

4.1. Sample Size

Provide justification of the sampling procedure and sample size. Delineate methods used to estimate the required number of subjects.

The estimated time +/- SD for the control and study groups is estimated at 30 +/- 15mins and 15 +/- 5 mins, respectively. Using a power calculation to identify an 90% power, then 10 patients in each group will be required. If however, the study group mean is 20 mins, and the sd is 16 mins, then 33 patients per group would be required. Therefore, to account for drop out, and/or a mistake in any of the above assumptions, the plan is to aim for 50 patients in each group.

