4.2. Method of Data Analysis

Data collection will occur just prior to, and during the ablation procedure. Also, data will be collected at before hospital discharge after the procedure (usually the next day), and at the 1 month outpatient follow up visit. Data entry will be directly the statistical program, SAS. Continuous variables will be expressed as the mean +/- SD. Univariate comparisons will be performed on continuous variables with either paired or unpaired T test, or analysis of variance, as appropriate. Categorical variables will be compared with Chi-square analysis. Statistical significance will be considered present with a p value ≤ 0.05 . Please see section 4.1 above for the power calculation.

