5. HUMAN SUBJECTS PROTECTION (RISKS, BENEFITS, AND ALTERNATIVES)

5.1. Risks

Potential loss of privacy. The risk will be minimized by shielding the participant by unlinking his or her identity from his or her personal health information.

Physical risk. Both techniques to obtain hemostasis are utilized clinically. Each technique to obtain hemostasis may be associated with minimal pain or discomfort (3/100), or associated with bleeding or vessel complications (5/100). These risks are intrinsic to an ablation procedure for AF, and participation in the study will not elevate or reduce these risks.

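### Groin complications are part of the hypothesis, but on sparse counts a chi-square p-value alone will say little; report one per-patient outcome as a risk difference with a 95% confidence interval

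*Combined protocol and SAP*

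**What the plan says.** The hypothesis in section 1.2 has two parts: the suture will take less time, and it will "be associated with a lower frequency of groin complications". Section 1.1 gives the goal as a comparison of safety and efficacy.

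The endpoint sections rank the two parts differently. Two times are primary (section 3.4.1). Complications come second: "Secondary end points include groin complications including bleeding, hematoma, pseudoaneurysm, and transfusion" (section 3.4.2). The Study Methodology paragraph of the abstract has a longer secondary list, which also contains "additional pressure required for hemostasis, hematoma, pseudoaneurysm, and transfusion". Additional pressure appears only there.

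The analysis plan for these outcomes in section 4.2 is short: "Categorical variables will be compared with Chi-square analysis", and "Statistical significance will be considered present with a p value ≤ 0.05". The abstract plans the same. The available text gives no risk difference, confidence interval or margin for complications, and no rule for combining the components into one result per patient.

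Section 4.1 bases the sample size on a time only and concludes that "the plan is to aim for 50 patients in each group". The one complication rate is in the human-subjects section, 5.1, where either technique may be "associated with bleeding or vessel complications (5/100"). That section adds that "participation in the study will not elevate or reduce these risks".

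**The concern.** A directional statement about complications is paired with an analysis that yields only a p-value, on what may be a handful of events. Two consequences follow. First, if events are as rare as section 5.1 suggests, the test would usually miss even a complete removal of complications. Second, a p-value above 0.05 does not tell the reader whether a large benefit or a large harm is still possible. Section 1.3 says that the two techniques have never been compared directly, so the range of differences still compatible with the data is the useful safety result.

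Because no per-patient outcome is defined, the plan also permits a separate chi-square test on each component, which would divide about five expected events still further.

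**Working it through.** **Inputs.** 50 patients per arm (section 4.1), allocated 1:1 (section 3.2). Chi-square at 0.05 (section 4.2); two-sided is my assumption, and the section does not say whether a continuity correction applies. Rate 5/100 (section 5.1). The protocol states no complication rate for the suture arm that differs from the manual arm, so every contrast below is an assumption.

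**The plan's own figure.** There is none for complications. The sample sizes in section 4.1 concern time. The first reproduces with the mean of the two SDs, (15 + 5)/2 = 10, and a difference of 30 − 15 = 15 min: n = 2 × (1.960 + 1.282)² × 10² / 15² = 9.3, so 10 per group. The second (33 per group) does not reproduce from its stated inputs by this method: SDs 15 and 16 give a mean of 15.5, and with a difference of 10 min n = 2 × (1.960 + 1.282)² × 15.5² / 10² = 50.5, so 51. That is a separate matter and does not affect this point.

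**Expected events.** 50 × 0.05 = 2.5 per arm, 5 in the trial.

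**Smallest significant split with no events in the suture arm.** For 4/50 versus 0/50, uncorrected chi-square = 100 × (4 × 50 − 0 × 46)² / (50 × 50 × 4 × 96) = 4.17, p = 0.041. For 3 versus 0, p = 0.079. At 4 versus 0 the expected event count is 2 per arm, where the chi-square approximation is poor: Yates gives p = 0.126 and Fisher p = 0.117. Fisher first reaches significance at 6 versus 0 (p = 0.027).

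**Power if the suture removes every complication.** With zero suture events, power is the chance that the manual arm has enough of them:
- uncorrected: P(X ≥ 4 | 50, 0.05) = 0.240
- Fisher: P(X ≥ 6 | 50, 0.05) = 0.038

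**Power for other contrasts.** Power = Σ P(X₁ = i) P(X₂ = j) over all pairs (i, j) with p ≤ 0.05, where X₁ and X₂ are binomial with n = 50.

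| Manual vs suture (assumed) | Uncorrected chi-square | Fisher |
|---|---|---|
| 5% vs 2.5% | 7.5% | 1.2% |
| 5% vs 1% | 14.9% | 2.4% |
| 5% vs 0% | 24.0% | 3.8% |
| 10% vs 5% | 14.5% | 6.3% |
| 10% vs 0% | 75.0% | 38.4% |
| 15% vs 5% | 39.3% | 24.4% |
| 20% vs 5% | 66.4% | 50.8% |

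**What an interval would show.** The Newcombe limits for d = p₁ − p₂ combine the Wilson limits (l, u) of each arm: lower = d − √[(p₁ − l₁)² + (u₂ − p₂)²]; upper = d + √[(u₁ − p₁)² + (p₂ − l₂)²]. For 3/50 versus 2/50 the Wilson limits are 0.0206 to 0.1622 and 0.0110 to 0.1346.
- Lower: 0.02 − √[(0.06 − 0.0206)² + (0.1346 − 0.04)²] = −0.082
- Upper: 0.02 + √[(0.1622 − 0.06)² + (0.04 − 0.0110)²] = 0.126

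The estimate is +2 points, with an interval from −8.2 to +12.6. Similarly, 2/50 versus 1/50 gives −7.0 to +11.6, and 3/50 versus 3/50 gives −10.9 to +10.9. For 4/50 versus 0/50, where uncorrected chi-square is significant, the interval is −0.6 to +18.8 and includes zero.

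**The case against.** The strongest reply is that complications are secondary. A trial is normally sized on its primary endpoint, and low power for a secondary safety outcome in a 100-patient, single-center study is common. This stands: a reader might infer that the sample size is wrong or that more patients are needed, but the endpoint hierarchy does not support that.

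Next, the 5/100 is a risk disclosure for bleeding or vessel complications, not a rate for the endpoint. The abstract's list includes additional pressure, which could be more frequent. This also stands. It is why the table goes above 5%, and why it would be too strong to say that the comparison is bound to be non-significant.

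A reader might also infer that the chi-square test cannot confirm the hypothesis at all. The 4 versus 0 split at p = 0.041 contradicts that; the fair statement is low power and an unreliable approximation. Nor does any passage plan an equivalence or equal-safety claim. That risk lies in how a non-significant result may later be read and is not an error in the text.

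Finally, an interval of roughly ±10 points around a 5% rate does not settle the safety question either, and anyone could calculate it from published counts. True, but it states the uncertainty that a p-value hides. Planning it in advance also fixes the outcome definition before the data are seen.

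**Conclusion.** The point holds as a reporting and analysis weakness in a secondary outcome. If the manual-arm rate is near 5%, power for a benefit of the suture is at most 24% with uncorrected chi-square and 3.8% with Fisher at 50 per arm, so a non-significant result is likely. If the abstract's wider list has a higher rate, power could reach 39% (15% versus 5%) or 66% (20% versus 5%). These contrasts are assumptions, because the protocol gives neither a rate for its complication endpoint nor an expected effect. In all of these cases a p-value alone leaves unreported which differences remain possible.

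It does not follow that the directional hypothesis in section 1.2 must be removed. Nothing labels its complication part confirmatory, and keeping it is a matter of preference once complications are clearly identified as secondary and are estimated.

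**What to change.** In section 4.2:

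1. Reconcile the complication lists in the abstract and section 3.4.2, deciding whether additional pressure counts. This comes first, because it may drive the event rate.
2. Define one outcome per patient: any groin complication by the 1-month visit, with its components named.
3. Report it as a risk difference (manual minus Figure of 8) with a 95% Newcombe confidence interval.
4. List the components as counts per arm, without separate tests.
5. If a p-value is kept, use Fisher's exact test.
6. State that a non-significant difference will not be read as equal safety.

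Section 1.2 may stay, provided that complications are labelled there as secondary and to be estimated.

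The cost is a few sentences. No patients or visits are added, since complications are already assessed the day after the procedure and at 1 month. The downside is that the interval will be wide, about ±10 points at these rates, so the safety conclusion will be modest.

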1.3. Background and Significance

Ablation for AF is a common procedure and is considered first line therapy in many patients with symptomatic paroxysmal AF (1). The goal of AF ablation is to electrically isolate the pulmonary veins, which are attached to the left atrium. The procedure involves obtaining femoral vein access, usually with 2 access sites in each groin. The sheath sizes vary varies, depending on a variety of factors. However, when the cryoballoon is used, it requires a 12 Fr sheath. Three other smaller sheaths are also used. Usually, a 7 FR, 8 FR and 9Fr sheath are utilized. To access the left atrium, a transeptal puncture is required. To prevent thrombus formation and systemic emboli from occurring during the ablation procedure, heparin is administered to maintain the ACT > 300 seconds (1). Protamine is administered at the time the figure of 8 suture is placed to reverse the heparin after an ACT is obtained. The

protamine dosage is determined by the operator. After protamine is administered, the ACT is rechecked, and if < 220 msec, the sheaths are pulled. Hemostasis is often achieved with manual pressure (2). Alternatively, the use of a Figure of 8 suture can also be used to achieve hemostasis in anticoagulated patients, and obviates the need for reversing heparin with protamine. After catheters are removed, a silk suture is placed in a figure of 8 around each pair of sheaths. The sheaths are removed as the suture is cinched down, and tied firmly. The suture is removed at least 6 hours later.

Problems with venous access and hemostasis are the most common complications with AF ablation (1-2). There are no direct comparisons of manual compression versus the figure of 8 technique to achieve hemostasis after AF ablation. It is unknown if one or the other technique is better, associated with fewer complications, or requires less time to achieve hemostasis.

This study will randomize 100 (50 in each group) patients undergoing Cryo balloon for AF to manual (Manual Hemostasis Group) or figure of 8 (Figure of 8 Hemostasis Group) hemostasis. We will assess the time required for each technique, the time until the patient can leave the lab, and evaluate for groin complications that may occur during follow up.

1.4. Preliminary Studies

There are no preliminary studies that the Principal Investigator/Sub-Investigator (PI/SI) have performed to establish the experience and competence of the PI/SI to pursue this project. However, all of the PI/SI have clinical experience with both techniques to achieve hemostasis after an AF ablation.

2. STUDY DESIGN AND SUBJECT SELECTION

2.1. Study Type

This is a randomized, not blinded study of two standard of care techniques used to obtain hemostasis after an AF ablation procedure..

2.3. Duration of Study

The study begins on the day of the AF ablation and ends at the 1 month outpatient follow up visit. Therefore, the subjects are required to continue in the study for 1 month. No biological specimens are collected for this study.

2.4. Number of Subjects

State the total number of subjects expected to participate. For multi-center protocols, this should include both the overall total and the number of subjects to be enrolled at each site.

This single center study is expected to include 100 patients.

2.5. Study Population

2.5.1. Gender of Subjects

Subjects of both genders will be able to participate.

2.5.2. Age of Subjects

Any subject 18 years or older, will be eligible to participate.

2.5.3. Racial and Ethnic Origin

Patients of any race and ethnicity will be eligible to participate.

2.5.4. Vulnerable Populations

Vulnerable populations are excluded. Specifically, patients who are pregnant, <18 years old, prisoners, and those who cannot provide informed consent in English will be excluded.

2.6. Recruitment

We will not advertise for subjects, there will be no recruiting materials—telephone or speech script, email or letter text, or advertisements or flyers. When patients are seen and they agree to undergo ablation of AF using the Cryoballoon, they will be asked if they wish to participate in this study.

2.7. Inclusion Criteria

Any patient who meets standard clinical criteria for an ablation of AF with Cryoballoon, and is to undergo the procedure, will be eligible to participate in this study; as long as they do not meet the exclusion criteria delineated below.

2.8. Exclusion Criteria

1. Pregnant patients.
2. Age <18 years.
3. Patients who cannot provide consent in English.
4. Prisoners.

3. STUDY METHODS AND PROCEDURES

3.1. Study Treatment/Intervention

See above. Besides the randomization, there will be no experimental procedures performed.

No drug or device that is investigational under FDA policy will be utilized. The figure of 8 technique to achieve venous hemostasis utilizes a silk suture that is FDA approved and is on the “shelf”.

After the patient agrees to have an AF ablation with the cryoballoon, they will be asked to participate in this trial. If they agree, consent will be obtained. The ablation is usually performed 2 weeks to 3 months after being seen in the office. They will be seen by an investigator the morning after the ablation procedure, and again 1 month later.

3.2. Control Group

Is there a control group? The control group may be receiving no treatment or a standard treatment. Will randomization be required?

Patients will be randomized 1:1 to either the Manual Hemostasis Group (Control) or to the Figure of 8 Hemostasis Group.

3.3. Randomization

Patients will be numbered as they are randomized into the study. For instance, the first patient randomized, will be patient 001, and so on. The IHVI Research Center will serve as the randomization center. When the procedure is to begin, the randomization will be

provided. Randomization will be performed by a random number generator. Patients who receive an odd number, will be randomized to the control group, i.e., manual hemostasis.

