3.4. Endpoints/Outcomes Measurements

3.4.1. Primary outcomes.

The primary short term study endpoints will be the time required for hemostasis, and the time required from the end of the ablation procedure until the patient leaves the EP Lab.

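### Minor, cheap improvement: the allocation is released before the ablation although the described arm-specific steps come at the end, and the protocol body names no time-stamped start for the second primary endpoint, so knowledge of the arm could influence it

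*Combined protocol and SAP*

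**What the plan says.** **Release of the arm.** Section 3.3 makes the research center responsible ("The IHVI Research Center will serve as the randomization center") and sets the time of release: "When the procedure is to begin, the randomization will be" provided. The Day 2 column of the appendix flowchart lists randomization, then ablation, then the ablation form.

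**Arm-specific steps.** Section 1.1 places hemostasis after the ablation in both arms: "At the conclusion of the procedure, the venous sheaths are removed and hemostasis is obtained". For the manual arm, "In the manual hemostasis approach, an ACT is checked and protamine is administered", followed by sheath removal and pressure. For the suture arm, section 1.3 says "After catheters are removed, a silk suture is placed in a figure of 8 around each pair of sheaths".

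**Blinding.** Section 2.1: "This is a randomized, not blinded study of two standard of care techniques used to obtain hemostasis after an AF ablation procedure". Section 3.6 repeats that the study is not blinded and adds that no monitor will be used.

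**Start of the second primary endpoint.** The abstract (Study Methodology) gives "the time required from the completion of the ablation portion of the procedure until the patient leaves" the EP lab. Section 3.4.1 gives "the time required from the end of the ablation procedure until the patient leaves the EP Lab".

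**The concern.** Nothing described in the protocol requires the arm to be known during the ablation, and no reason for early release is given. Early release means that whoever declares or records the end of ablation can know which technique will follow. The two descriptions of that moment leave room for judgement: the last cryo application, withdrawal of the catheter and the end of the case could each fit.

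The hypothesis in section 1.2 is directional, since the suture is expected to be faster. A start recorded somewhat later in the suture arm, or a brisker wind-down of the ablation once the arm is known, would favour that hypothesis without any effect of the technique. In an open trial of this kind, hemostasis time and the moment of leaving the lab cannot be shielded from knowledge of the arm. The start of the clock can be.

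**Working it through.** The point rests on reading, not on a figure in the plan, so there is no stated number to reproduce.

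**Step 1: what procedure means in section 3.3.** Alone, the word could mean the hemostasis procedure. Section 1.1 uses it for the ablation: heparin is given during it and the sheaths come out when it concludes. The flowchart order agrees. Release before the ablation is the natural reading.

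**Step 2: whether any arm-specific step comes before or during the ablation.** None is described. The manual-arm steps belong to the end of the procedure, and the suture follows catheter removal. Two details are less tidy:
- Section 1.3 has protamine given when the suture is placed, and then says the suture makes reversal unnecessary. The abstract and section 1.1 also say the suture avoids protamine. These passages conflict, although on either reading the step comes at the end.
- No passage says that the manual-arm ACT check follows removal of the cryoballoon catheter. Catheter removal is therefore not shown to precede every arm-specific step.

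**Step 3: whether the start is operationally defined.** The two wordings name a moment but no observable event, recorder or time-stamp rule. The flowchart lists an ablation form, whose content is not in the text.

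**Step 4: illustration of sensitivity.** Inputs:
- 50 per arm (section 4.1) and the 0.05 threshold (section 4.2), taken as two-sided because sidedness is not stated.
- SD pairs 15/5 and 15/16 minutes (section 4.1, which does not say which time they describe).
- Assumed equal SDs of 20, 25 and 30 minutes.
- No true difference, and an assumed constant shift b of the recorded start in one arm.

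SE = √[(SD₁² + SD₂²)/50]. The noncentrality is b/SE, and the rejection rate comes from the noncentral t distribution with Welch degrees of freedom. For 15/5, SE = √(250/50) = 2.236 with 59.8 df. For 15/16, SE = √(481/50) = 3.102 with 97.6 df.

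| SDs (min) | SE | b = 2: b/SE | Rejection rate | b = 5: b/SE | Rejection rate |
|---|---|---|---|---|---|
| 15/5 | 2.236 | 0.89 | 14.2% | 2.24 | 59.5% |
| 15/16 | 3.102 | 0.64 | 9.8% | 1.61 | 35.8% |
| 20/20 | 4.0 | 0.50 | 7.9% | 1.25 | 23.6% |
| 25/25 | 5.0 | 0.40 | 6.8% | 1.00 | 16.8% |
| 30/30 | 6.0 | 0.33 | 6.3% | 0.83 | 13.1% |

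The shifts are assumptions. The table shows how the test would respond to a shift, not that one is likely.

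**The case against.** **Central randomization at the start of a case is a legitimate choice, and a logged start time would do most of the work.** This largely stands. Once the start is an objective logged event, it cannot easily be recorded differently by arm. Late release then adds protection only for conduct before that event. That is still a better method than the one stated in section 3.3, but the gain is modest.

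**Late release could create the problem it targets.** This stands as a real downside. The release step, and any wait for the right person, would fall inside the second primary interval. Section 10 has lab staff perform manual pressure and the physician place the suture, so the wait could differ by arm. A 2-minute differential delay would act exactly like the 2-minute shift in the table. Section 10 also says that personnel are routinely available, which makes late release plausible but does not establish that it is workable.

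**The ablation form may already define the time.** It may. The text supports only that the protocol body does not define it; a reader should not infer that the endpoint has no definition anywhere.

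**Aborted cases.** A reader might infer that early release costs power, because a patient whose cryoablation is aborted is already randomized and uses one of the 100 places. The documents do not support this. Such a patient may still need sheath removal and hemostasis and can be analysed, and no passage removes such patients from the analysis.

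**Conclusion.** The concern holds as a minor, inexpensive improvement. The arm is released before the ablation, the described arm-specific steps come at the end of the procedure, the trial is open, and the protocol body gives no time-stamped start for a primary endpoint. Together these leave an avoidable opportunity for knowledge of the arm to influence the start time and conduct at the end of ablation.

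Two stronger readings are tempting. One is that the second primary endpoint is biased: nothing in the documents shows this, and the size of any bias cannot be computed from them. The other is that the false-positive rate could be near 60%. That figure needs an assumed systematic 5-minute shift together with the 15/5 SD pair, which section 4.1 attaches to a scenario with unequal means and to an unspecified time. It is the extreme of the illustration; with SDs of 20 to 30 minutes, a 2-minute shift gives 6% to 8%.

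The conclusion assumes that procedure in section 3.3 means the ablation. If the ablation form does name an event, the definition needs only a citation, and the early release remains the point.

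**What to change.** 1. **One start event.** In the abstract and section 3.4.1, use identical words for one objective, logged event that the investigators confirm precedes the ACT check, protamine and suture in both arms. The logged end of the last cryo application is an example. If the ablation form already defines the event, cite it.
2. **Later release.** In section 3.3 and the flowchart, have the research center release the allocation only after that time is recorded, at once and by the same route in both arms, with staff for both techniques ready beforehand. Record the release time so that any delay can be compared between arms.
3. **Feasibility.** Have the investigators confirm that late release works in their lab. If it does not, keep item 1 alone.
4. **Protamine.** Reconcile the passages on protamine in the suture arm (section 1.3 against the abstract and section 1.1), so that the steps the start event must precede are clear.

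The cost is a short amendment, with no extra patients, visits or tests. An equal constant delay leaves the difference between arms unchanged. A delay that varies by chance, equally in both arms, costs little: for 30 versus 20 minutes with SDs 15/16, power at 50 per arm is 89.1%. An assumed delay SD of 2 minutes (SE = √[(481 + 2×4)/50] = 3.13) gives 88.6%, and an SD of 5 minutes (SE = √[(481 + 2×25)/50] = 3.26) gives 86.0%. These figures assume that the section 4.1 SDs apply to this endpoint. A delay that differed by arm would bias it, which is why the release time should be recorded. Randomizing fewer patients whose cryoablation is aborted is a minor side benefit only. Hemostasis time and the moment of leaving the lab remain unblinded.
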